## 2) Objectives

**Primary Objective:** To culturally tailor a technology-based individualized adherence intervention for Black and Latino patients with uncontrolled HTN or T2DM, who are non-adherent to their medications, and determine its acceptability.

**Secondary Objective:** To assess the feasibility of the methods and procedures to implement the individualized adherence intervention within a primary care practice in New York City.

**Tertiary Objectives:** To compare the efficacy of a tailored adherence intervention to a single patient education (PE) session on:

- a. Change in medication adherence at 3 months.
- b. Blood pressure (BP) reduction at 3 months.
- c. HbA1c reduction at 3 months.

**Hypotheses:** Among 40 Latino and Black patients with uncontrolled hypertension (HTN) or type 2 diabetes those randomized to the intervention, compared to those randomized to PE, will:

- a. Exhibit higher rate of adherence to their antihypertensive or anti-diabetic medications at 3 months.
- b. Exhibit a greater reduction in systolic and diastolic BP at 3 months.
- c. Exhibit a greater reduction in HbA1c at 3 months.

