### **Analysis for the Tertiary Aims:**

**The effect of treatment on adherence status at 3-months.** Adherence will be measured as a continuous variable. A linear regression will be performed using the final assessment of adherence as a response and randomization group as a predictor. Other variables that may potentially have an effect on adherence such as age, gender, level of education and comorbidity will also be included if these variables are not balanced between groups by the randomization or if they are determined by univariate analysis to be significantly predictive of adherence.

**The effect of treatment on BP reduction at 3-months.** BP will be treated as continuous systolic BP (SBP) and diastolic BP (DBP) variables measured at baseline and 3-months. The effect of treatment on these variables over time will be assessed using differences in differences estimation whereby pre-intervention SBP and DBP values are subtracted from post-intervention values, and change amounts by study group are compared using t tests. The significance level will be set at  $\alpha=.05$ . Analysis of covariance will be used in place of a t test, if covariates are needed.

**The effect of treatment on HbA1c reduction at 3-months.** HbA1c will be treated as a continuous variable at baseline and 3 months. The effect of treatment on HbA1c over time will be assessed using differences in differences estimation whereby pre-intervention HbA1c values are subtracted from post-intervention values, and change amounts by study group are compared using t tests. The significance level will be set at  $\alpha=.05$ . Analysis of covariance will be used in place of a t test, if covariates are needed.

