**Data Management:** [name] will oversee the data management for this study. All data will be double entered by RAs and compared using automated comparison programs. Inconsistent data entry will be resolved against the raw data, and comparisons will continue until all inconsistency is removed. Periodically, [name] will review all data for duplicate records, illogical collection dates and contingencies, and outlier values using program syntax created for each file. Reasons for dropout and loss to follow-up will be tabulated by condition. The results of analyses using imputed values will be compared with the results obtained with only complete cases. If the results indicate that attrition is significantly related to one or more baseline variable, predicted values from a logit model will be used as a covariate in all subsequent analyses, thereby correcting for differential attrition. All randomized participants will be included using intent-to-treat analytic strategies. While randomization is expected to produce well-balanced groups, analyses will determine baseline differences between the groups on demographic or prognostic variables. If significant differences are found, these variables will be included in a logit model to predict group assignment, and predicted values from the final logit model will be used as a covariate in all subsequent analyses.

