Statistical Analytic Plan
Tailored Approaches to Improve Medication Adherence
NCT01643473
05/10/2018

Analysis of the qualitative data: [name] and a trained research assistant conducted the qualitative analysis of the audiotaped interview data. Transcripts of the interviews were uploaded to the Atlas.ti program in order to code the data and facilitate content analysis. The transcripts were individually reviewed and analyzed using the grounded theory constant comparison method. Specifically, transcripts were coded line-by-line using open coding (comparing and categorizing data to generate concepts); axial coding (reorganizing data into categories based on relationships within and between these categories); and selective coding (identifying and describing the central themes to generate a conceptual framework) according to issues related to medication-taking (e.g., side effects, cost, forgetfulness). Once the transcripts were independently coded, the research team met to discuss the coding and resolve any discrepancies.

Analysis of study feasibility: We assessed reach of the intervention by examining the ratio of eligible participants invited to participate vs. those that enroll in the study. We also collected data on patients' age and gender to determine if there are any differences between eligible participants that do not enroll vs. enrollees. Independent t-tests and the chi-square statistic were used to determine if there are any significant differences between the groups. Reasons for not enrolling in the program were also documented. In addition to these outcomes, exit interviews were conducted with a subsample of 12 participants to assess acceptability and satisfaction with the program.

Analysis of exploratory outcomes: To test the exploratory aim, we conducted separate differences in differences estimations for each of the outcome measures (i.e., adherence, BP HbA1c) whereby pre-intervention values are subtracted from post-intervention values, and change amounts by study group are compared using t tests. We also conducted linear regression models to examine whether the average baseline scores were significantly different from the average scores at 3 months, when, controlling for baseline levels of the outcome measure (i.e., adherence, BP HbA1c), age, gender socioeconomic status (SES), insurance status and number of medications

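### The SAP's only covariate-adjusted model is worded as a test of baseline against 3 months and names no study-group term, so as written it does not estimate TAI versus PE

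*SAP*

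**What the plan says.** The tertiary aim is between-arm. Protocol section 2 states it as "To compare the efficacy of a tailored adherence intervention to a single patient education (PE) session on" medication adherence, BP and HbA1c at 3 months.

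The SAP paragraph on exploratory outcomes gives two analyses:

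- **Unadjusted.** Differences in differences, in which "change amounts by study group are compared using t tests".
- **Adjusted.** "linear regression models to examine whether the average baseline scores were significantly different from the average scores at 3 months", "controlling for baseline levels of the outcome measure (i.e., adherence, BP HbA1c), age, gender socioeconomic status (SES), insurance status and number of medications". Study group is not in that list, and no response variable is named.

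The SAP contains no other covariate-adjusted model.

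Protocol section 10 (Analysis for the Tertiary Aims) is more explicit. For adherence: "A linear regression will be performed using the final assessment of adherence as a response and randomization group as a predictor". For BP and HbA1c, change is compared between groups by t test, and "Analysis of covariance will be used in place of a t test, if covariates are needed".

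**The concern.** A test of whether the average moved between baseline and 3 months does not compare TAI with PE. It pools both arms, so anything that shifts all patients counts as signal: time, clinic attention, or regression to the mean. It can also miss a real arm difference when the arms move in opposite directions.

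The design makes the first problem concrete. Under protocol section 9, the mean of three BP readings at the first visit is both an entry screen and the baseline value. HbA1c and the Morisky adherence score are screened at that same visit. Patients picked for being on one side of a cut-off tend to drift back at the next measurement without any treatment effect. Randomised arms share that drift, so a between-arm comparison is protected and a pooled comparison is not.

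At stake is the meaning of any adjusted p-value reported under this SAP: does it concern TAI versus PE, or everyone's change since baseline?

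**Working it through.** The documents give no figure to reproduce here. The point rests on the text, and the simulations only show why the reading matters.

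**1. What the sentence can mean as a model.** Let Y0 be the baseline value, Y1 the 3-month value and G the study group.

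- *Literal reading.* If Y1 is regressed on Y0 and covariates, no coefficient tests Y0 against Y1. A coherent form is Y1 − Y0 = a + c(Y0 − mean Y0) + covariates, testing a, which is the pooled mean change. This form is my construction; the SAP does not write it out.
- *Likely intent.* Y1 = a + bG + cY0 + covariates, testing b, the adjusted TAI-versus-PE difference. Using change as the response gives the same b, since Y1 − Y0 = a + bG + (c − 1)Y0 + covariates. Once Y0 is in the model, the important omission is G.

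**2. What each reading does.** Assumed: 15 per arm, SD 1, baseline to 3-month correlation 0.5, two-sided 5% level, 4,000 simulated trials per scenario.

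| Scenario | Pooled paired test | No-group regression | Y1 on Y0 and G |
|---|---|---|---|
| Common change 0.5 SD, arms equal | 75% | 83% | 4.8% |
| Common change −0.4 SD, arm difference 0.8 SD (pooled change −0.4 + 0.8/2 = 0) | 3% | 5% | 68% |

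The literal model can be significant when the arms are equal and silent when they differ.

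**3. How much drift entry screening alone could produce: systolic BP (SBP), no treatment effect.**

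- From the protocol: entry at baseline is SBP ≥140 or DBP ≥90 (section 9). Earlier visits are judged at 140/90, or at 130/80 with diabetes or kidney disease (section 4). Completers are 15 per arm as stated, or 20 × 0.85 = 17 (section 10).
- Assumed, because the documents give none: SBP mean 135–145 and SD 18; DBP mean 82 and SD 11; SBP–DBP correlation 0.6; visit-to-visit correlation 0.5–0.7.

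| Earlier-visit rule | SBP fall, all BP-selected | Pooled pre-post test significant, all selected | Same test, half not BP-selected |
|---|---|---|---|
| 140/90 | 1.7–4.5 mmHg | 10%–33% | about 6%–11% |
| 130/80 | 2.6–6.0 mmHg | 17%–52% | about 6%–16% |
| No earlier BP selection (qualified on HbA1c) | 3.1–7.3 mmHg | 23%–69% | about 10%–20% |

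The change-score t test by arm stays at about 5% throughout. With no entry selection, the pooled test is also at about 5%.

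The last two columns are both needed because the documents differ on entry. Section 9 requires raised BP *and* raised HbA1c to go further, whereas sections 2, 4 and 8 describe hypertension *or* diabetes. Under *and*, every patient is selected on BP. Under *or*, some are not and the drift is diluted. The half share is an assumption. Those passages need reconciling; this point takes no side.

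**4. Does the protocol resolve the SAP sentence?** On arm contrast or not, yes. The adherence regression has randomization group as a predictor. The BP and HbA1c analysis of covariance replaces a t test that is itself between-group. The logit-based covariate in the data management text of section 10 would be added to those analyses, not replace them. None of these is a pooled pre-post model. The protocol leaves two narrower matters open: the form of the response in the adjusted model, and whether baseline adherence enters the adherence model.

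**The case against.** The strongest reply is that this is only a loosely phrased analysis of covariance. The SAP paragraph opens by tying its analyses to the exploratory aim, the regression follows directly on a comparison by study group, and adjustment for baseline fits analysis of covariance while making the literal test incoherent. The protocol's efficacy models all compare arms. All of this stands, and it makes analysis of covariance the more likely intent. It does not remove the gap: the SAP states a purpose for the model, that purpose is baseline against 3 months, and it does not refer back to the protocol's specification.

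A second reply is that the simulated rates depend on a test the SAP does not write out and on assumed inputs. That also stands. The higher rates further require every patient to have been selected on baseline BP, so they are illustrations and not estimates for this trial.

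Three stronger readings are tempting, and the documents do not support them:

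- *The SAP has no valid arm comparison.* It has one, the t test of change by study group.
- *The protocol leaves it unclear whether an arm contrast was intended.* Its efficacy models are all between-arm.
- *The group term was left out of the fitted model.* The SAP is written in the past tense but shows no fitted model, so this cannot be known from the text.

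**Conclusion.** The point holds as a minor one. As written, the SAP's adjusted model is a pooled baseline-to-3-month test and does not answer the TAI-versus-PE question. A between-arm analysis of covariance was probably meant but is not stated.

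If the literal model was used, chance of a significant SBP result without any treatment effect is about 10% to 70% when all patients are selected on baseline BP, and about 6% to 20% when half are not, against about 5% for the arm comparison. These ranges are for the simple pooled pre-post test and rest on the assumed means, SDs and correlations above, with 15 to 17 per arm. The textual finding needs none of them.

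The harm is limited. The outcomes are exploratory, the protocol makes no power claim for this pilot, and the unadjusted t test already compares the arms.

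**What to change.** In the SAP, state the adjusted model for adherence, SBP, DBP and HbA1c as: 3-month value = study group + baseline value of that outcome + the covariates the SAP already lists (age, gender, SES, insurance status, number of medications). Report the study-group coefficient with its 95% confidence interval as the adjusted TAI-versus-PE estimate.

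Keep the change-score t test by study group. Do not present pooled baseline-to-3-month tests as evidence that TAI works.

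If the model that was fitted already had a group term, say so; nothing needs re-running. If it did not, re-run it with one and label the result post hoc.

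The cost is one sentence in the SAP and, at most, a re-run on data already collected. This point needs no protocol change.
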